#### 9.6. Pregnancy Testing

To ensure participant safety, each pregnancy must be reported to Sponsor within 24 hours of learning of its occurrence and the study drug must be discontinued. Serum and urine pregnancy

tests will be performed for female participants only at the visits specified in the schedule of events (see Appendix 15.1). Pregnancy test results will be presented in a listing for the SAS.

#### 9.7. Columbia-Suicide Severity Rating Scale (C-SSRS)

The C-SSRS is utilized to prospectively assess and directly classifies suicidal ideation and behavior into 11 categories (five subtypes of suicidal ideation, five subtypes of suicidal behavior, and self-injurious behavior without suicidal intent). The C-SSRS assesses lifetime and current suicidal thoughts and behaviors across these categories based on an increasing severity of a 1 to 5 rating scale. The C-SSRS assessments will be done at the visits specified in the schedule of events (see Appendix 15.1). Summary table of the scores for suicidal ideation, suicidal behavior, and self-injurious behavior without suicidal intent and suicide-related treatment-emergent events will be presented by the worst score for the SAS by treatment group. Shift tables for categories (No suicidal ideation or behavior/Suicidal ideation/Suicidal behavior) and suicidal ideation Scores will also be presented. Only during treatment endpoints including unscheduled assessments are used in the summary outputs.

Two listings (complete and simplified) will be displayed for the SAS.

#### **10. Pharmacokinetics**

Plasma samples for concentration of DC-806 obtained from participants who receive DC-806 at various time the following timepoints after the first administration of study drug will be analyzed for the concentration of DC-806 by a validated method:

Day 1: pre-dose, 0.5h, 1h; Day 8: pre-dose; Day 15: pre-dose, 0.5h, 1h, 4h; Day 29: pre-dose; Day 57: pre-dose, 0.5h, 1h, 4h; Day 85: 12 h after Day 84 evening dose.

Individual plasma concentrations will be presented in data listings and summarized separately using descriptive statistics (number of observations, arithmetic mean, SD, CV, median, minimum, and maximum) by treatment group, study day and time point.

Individual plasma concentrations will be plotted by actual time on both linear and semi-logarithmic scales. Mean plasma concentrations will be plotted by treatment group on both linear and semi-logarithmic scales with all treatment groups overlaid on the same plots.

Standard PK parameters will be derived by noncompartmental analysis using Phoenix® WinNonlin® Version 8.3 or higher (Certara USA, Inc., Princeton, NJ) if sufficient data are available. The following PK parameters will be calculated for DC-806, where data permits: including trough concentration (Pre-dose concentration, Ctrough). Descriptive statistics will be presented for the analysis.

Summary statistics will be tabulated for maximum observed concentration ( $C_{max}$ ) and time to attain maximum observed plasma ( $t_{max}$ ) on Day 1, 15 and 57, Area under the curve from pre-dose to 4-hour post-dose (AUC0-4) on Day 15 and 57 and Ctrough levels will be reported on day 1,8,15, 29 and 57 schedule of visits (see Appendix 15.1) for the PK Set.

Ctrough	Concentration at the end of the dosing interval (pre-dose concentration following the first dose, on Days 8, 15, 29 and 57).
C max	Maximum observed concentration (Day 1, 15 and 57).
t max	Time of maximum observed concentration.
AUC 0-4	The area under the concentration time curve from time zero to time 4 hours post-dose (Day 15 and 57)

Actual sampling times will be used for the estimation of PK parameters.

Plasma PK parameters will be presented in data listings and summarized separately using descriptive statistics (number of observations, arithmetic mean, SD, CV, geometric mean, geometric CV, median, minimum, and maximum) by study day.

Plasma concentrations that are below the limit of quantification (BLQ) will be treated as zero for calculation of concentration descriptive statistics. For PK analysis, all BLQ values will be treated as zero, with the exception of BLQ values observed between 2 quantifiable concentrations which will be set to missing.

All PK outputs will be based on the PK Set. Data rounding specifications for PK data are documented in the PK TLF shells.

A listing of all plasma samples collected will also be presented.

#### **11. Pharmacodynamics**

These analyses are outside the scope of the study SAP.

#### **12.** Changes from the Planned Analysis

No change.

### **15. Appendices**

# 15.1. Schedule of Study Procedures

Procedure	Screening D-28 to D-1	D1ª	D8 ±2 days	D15 ±2 days	D29 ±2 days	D57 ±3 days	D85 b ±3 days or ET	Follow-up Visit D115 ±7 days
Informed consent c	X							
Inclusion /exclusion criteria	X	Х						
Pregnancy test d	X	Х			X	X	X	Х
Medical history and demographics e	X							
Columbia-Suicide Severity Rating Scale (C-SSRS) f,g	X	Х	X	X	X	X	X	Х
Dermatology Life Quality Index (DLQI) g		Х			X	X	Х	Х
Itch NRS g		Х	X	X	X	X	X	Х
Skin Pain NRS g		Х	X	X	X	X	X	Х
Concomitant medications h	X	Х	X	X	X	X	X	X
Monitor adverse events i	X	Х	X	X	X	X	X	X
Review daily dosing diary for compliance j			X	X	X	X	X	
Vital signs k	X	Х	X	X	Χ	Χ	X	Х
Height, weight, body mass index	Х							
Weight only		Х			X	X		Х
Electrocardiogram (12-lead) 	Х						X	Х
Triplicate electrocardiogram (12-lead) 1,m		Х		X		X		
Full physical examination	X	Х			X		X	
Targeted physical examination			X	X		X		X
Psoriasis Area and Severity Index score assessment	X	X	X	X	X	X	X	X
Body surface area assessment	X	Χ	X	X	X	X	X	X
Static Physician's Global Assessment	X	X	X	X	X	X	X	X

DICE Therapeutics, Inc. DCE806201

Procedure	Screening D-28 to D-1	D1ª	D8 ±2 days	D15 ±2 days	D29 ±2 days	D57 ±3 days	D85 b ±3 days or ET	Follow-up Visit D115 ±7 days
Medical skin photography n (selected sites only)		Х			X		X	
Skin biopsy n (selected sites only)		Х					Xº	
Urinalysis	X	Χ	X	X	X	X	X	Х
Hematology including CBC with differential	Х	Χ	X	X	X	X	X	Х
Chemistry panel	X	Χ	X	X	X	X	X	Х
High sensitivity C-reactive protein		Χ			X	X	X	
Fasting lipid panel p		Χ					X	
Fasting plasma glucose p		Χ					Χ	
Serology q	Х							
TB test r	X							
COVID-19 antigen test (nasal swab)	Χ	Χ						
Follicle stimulating hormone (postmenopausal women only)	Х							
Blood pharmacokinetic sampling s		Х	X	X	X	X	X	
Clinical pharmacodynamic sampling t		Х	X	X	X	X	X	
RNA Seq analysis (a subset of skin biopsy samples)		Х					X	
Immunohistochemistry assessment on biopsy samples		Х					X	
mRNA assessment on biopsy samples		Х					X	
Assign screening, participant, and IMP kit numbers in IRT "	X	Х		X	X	X		
Administer morning dose of study drug in clinic		Х	X	X	X	X		
Dispense study drug		Х		X	X	X		

CBC = complete blood count; COVID-19 = coronavirus disease 2019; C-SSRS = Columbia-Suicide Severity Rating Scale; D = Day; ET = early termination; HBcAb = hepatitis B core antibody; HBsAb = hepatitis B surface antibody; HBsAg = hepatitis B surface antigen; HCV Ab = hepatitis C virus antibody; HIV = human immunodeficiency virus; IMP = investigational medicinal product; IRT = interactive response technology; NRS = numerical rating scale; QFT-G = QuantiFERON®-TB Gold Plus panel; PROs = participant-reported outcomes; TB = tuberculosis; WOCBP = women of childbearing potential

a. All Day 1 study procedures must be performed before dosing on Day 1. Please refer to pharmacokinetic sampling schedule (Section 1.4) for predose and postdose timing.

b. Day 85 evaluations are performed in participants who have completed study treatment or are prematurely discontinued from study.

- c. A participant is considered enrolled only when the protocol-specific informed consent form is signed. Informed consent must be collected before completing any study procedures.
- d. A urine pregnancy test should be collected only for women considered by the Investigator to be of childbearing potential and before completing other screening procedures, see exclusion criteria in Section 5.2. Clinical human chorionic gonadotropin testing will be performed centrally to verify urine test results. All WOCBP must have a negative clinical pregnancy test prior to dosing on Day 1. Urine pregnancy testing will occur on Days 1, 29, 57, 85, and 115.
- e. Medical history includes any clinically significant diseases or procedures, and toxicities or allergies related to previous treatment.
- f. The C-SSRS 'Baseline/Screening' version is to be used at Screening and 'Since Last Visit' version is to be used for all other study visits.
- g. Participant-reported outcome assessments must be completed before all other clinical assessments (except at Screening). Refer to the Study Reference Manual.
- h. All medications used in the 28 days before screening through the end of study/early discontinuation visit must be recorded. In addition, all biologic treatments for psoriasis since diagnosis and all non-biological psoriasis medications /treatments used in the previous 5 years must be recorded (Section 6.7).
- i. After informed consent has been obtained, but before initiation of study drug, only serious adverse events caused by a protocol-mandated intervention should be collected and reported to the Sponsor. After initiation of study drug, all adverse events will be collected and reported to the Sponsor until the last follow-up visit. In addition, the Sponsor must be notified of any serious adverse events the Investigator becomes aware of that has occurred after the last follow-up visit and that is believed to be related to study drug.
- j. Please refer to the Study Reference Manual for compliance thresholds.
- k. Vital signs include body temperature (ear or oral), respiratory rate, seated blood pressure, and heart rate. Blood pressure and heart rate should be measured after the participant has been resting quietly for ≥5 minutes. Temperature should be measured using the same methodology throughout the study. Participants must refrain from using tobacco, caffeine or xanthine-containing for 30 minutes before vital signs being recorded.
- 1. 12-lead ECGs should be recorded after the participant has been supine for  $\geq$ 5 minutes. Safety ECGs will be read by the Investigator to determine any clinically significant abnormalities that would exclude the participant from further study participation (Section 5.2).
- m. 12-lead ECGs will be performed in triplicate, after the participant has been supine for ≥5 minutes, approximately 1 minute apart at predose and at 1 hour after dosing on Days 1, 15, and 57.
- n. Please refer to the Study Reference Manual.
- o. Skin biopsies are to be performed on Day 85 and are not required at the ET visit but may be collected at Investigator's discretion.
- p. Participants are required to fast for  $\geq 8$  hours before the collection of specimens.
- q. Serology includes HCV Ab, HBsAg, HBsAb, HBcAb, and HIV-1 and HIV-2 antibodies. Participants who are HBsAg negative, HBcAb positive, and HBsAb positive at Screening will have reflex testing for HBV DNA. Participants who are HCV Ab positive will have reflex testing for HCV RNA.
- r. Perform TB test procedure using the QFT-G. The QFT-G may be repeated once if the Investigator deems this to be necessary. A purified protein derivative test may be performed if central laboratory is unable to determine results of QFT-G. Should the purified protein derivative test be required, the test must be administered and evaluated by a health care professional 48 to 72 hours later. The test should be performed according to local standards with induration of <5 mm required for inclusion. If a negative purified protein derivative test has been documented in the 3 months before Screening, it does not need to be repeated.
- s. Pharmacokinetic samples are collected before the morning dose on Days 1, 8, 15, 29, and 57. Pharmacokinetic samples are collected postdose on Day 1 (at 0.5 and 1 hour after morning dose), Day 15 (at 0.5, 1, and 4 hours after morning dose), Day 57 (at 0.5, 1 and 4 hours after morning dose), and Day 85 (approximately 12 hours post Day 84 evening dose)
- t. All pharmacodynamic clinical samples must be collected before the morning dose

u. At Screening, obtain screening number through IRT. At Day 1, obtain participant number and IMP kit number through IRT. At Days 15, 29, and 57 obtain IMP kit numbers through IRT.

#### Pharmacokinetic Sampling Schedule

Study Day	Event	Sample Time (relative to dose) Hour: Minute (window)			
	Predose *	Within 2 hours before dosing			
1	Destiles	00:30 (±10 minutes)			
	Postdose	01:00 (±15 minutes)			
8	Predose *	Within 2 hours before dosing			
	Predose *	Within 2 hours before dosing			
15		00:30 (±10 minutes)			
15	Postdose b	01:00 (±15 minutes)			
		04:00 (±2 hours)			
29	Predose *	Within 2 hours before dosing			
	Predose *	Within 2 hours before dosing			
57		00:30 (±10 minutes)			
57	Postdose b	01:00 (±15 minutes)			
		04:00 (±2 hours)			
85	Postdose	Morning on Day 85, approximately 12 hours after Day 84 evening dose			

a. Predose samples must be drawn before the morning dose of study drug

b. Postdose samples (0.5, 1, and 4 hours after morning dose) on Day 15 and Day 57.

#### 15.2. PASI (Psoriasis Area and Severity Index score assessment)

The PASI quantifies the severity of a participant's psoriasis based on both, "lesion severity" and the "percent of body surface area (BSA)" affected. PASI is a composite scoring by the investigator of degree of erythema, induration, and scaling (each scored separately) for each of 4 body regions (head and neck, upper limbs, trunk [including axillae and groin], and lower limbs [including buttocks]), with adjustment for the percent of BSA involved for each body region and for the proportion of the body region to the whole body.

The PASI score ranges from 0 (no psoriasis on the body) to 72 (the most severe case of psoriasis), with higher scores reflecting greater disease severity. Erythema, thickness, and scaling are scored on a scale of 0 (none) to 4 (very severe) on 4 anatomic regions of the body: head, trunk, upper limbs, and lower limbs. Degree of involvement on each of the 4 anatomic regions is scored on a scale of 0 (no involvement) to 6 (90% to 100% involvement). The sum of severity scores for erythema, thickness, and scaling is multiplied by the degree of involvement for each anatomic region, and then multiplied by a constant corresponding to the region's percentage of body surface area (0.1, 0.3, 0.2, and 0.4 for the above 4 regions, respectively). The resultant values for each anatomic region are then summed to yield the PASI score. The PASI score will be set to missing if any severity score or degree of involvement is missing.

To be classified as a PASI-75 responder, a participant must achieve  $a \ge 75\%$  improvement from baseline. Percentage change from baseline will be rounded to one decimal place (i.e., xx.x%) and then compared to 75% to determine whether the required improvement is achieved.

The following formula is used to calculate the PASI score:

 $PASI = 0.1 (E_h + I_h + S_h) A_h + 0.2 (E_u + I_u + S_u) A_u + 0.3 (E_t + I_t + S_t) A_t + 0.4 (E_l + I_l + S_l) A_l$ Where E = erythema, I = inducation, S = scaling, A = area score, h = head/neck, u = upper limbs, t = trunk, and l = lower limbs.

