#### 8.1.1. Estimand 1a

#### 8.1.1.1. Main Analysis Approach

A participant receiving any prohibited medication or discontinuing the treatment due to related adverse event or requirement for prohibited medication prior to Week 12 visit will be considered as a non-responder (Composite strategy). If a participant discontinued treatment for reasons other than related adverse event or requirement for prohibited medication, PASI scores after the treatment discontinuation date will be set to missing (Hypothetical strategy). If a participant experienced any treatment interruption, PASI score reported after the treatment interruption will be used as reported (Treatment policy).

Participants without Week 12 PASI score (either due to hypothetical strategy implementation or missed visit) will be considered as non-responder.

A 2-sided, 2-sample Fisher's exact or Chi-squared test will be performed to assess a difference between active treatment groups (DC-806) versus Placebo in PASI-75 at Week 12 for the following comparisons on the FAS:

#### Comparison 1

H0: PASI-75 at Week 12  $_{DC-806\ 800mg}$  = PASI-75 at Week 12  $_{Placebo}$ H1: PASI-75 at Week 12  $_{DC-806\ 800mg} \neq$  PASI-75 at Week 12  $_{Placebo}$ 

#### Comparison 2

H0: PASI-75 at Week 12  $_{DC-806\ 600mg}$  = PASI-75 at Week 12  $_{Placebo}$ H1: PASI-75 at Week 12  $_{DC-806\ 600mg} \neq$  PASI-75 at Week 12  $_{Placebo}$ 

#### Comparison 3

H0: PASI-75 at Week 12  $_{DC-806 400mg}$  = PASI-75 at Week 12  $_{Placebo}$ 

H1: PASI-75 at Week 12  $_{DC-806 \ 400 mg} \neq$  PASI-75 at Week 12  $_{Placebo}$ 

#### Comparison 4

H0: PASI-75 at Week 12  $_{DC-806\ 200mg}$  = PASI-75 at Week 12  $_{Placebo}$ H1: PASI-75 at Week 12  $_{DC-806\ 200mg} \neq$  PASI-75 at Week 12  $_{Placebo}$ 

The number and percentage of participants who are defined as PASI-75 responder will be presented by treatment group. The p-value and unconditional odds ratio with its corresponding 95% CI will be presented in the active treatment group compared to the placebo group. All comparisons will be performed in a prespecified hierarchical procedure starting from the highest dose regimen to the lowest dose regimen.

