# 8.2.3. Proportion of participants achieving ≥50%, ≥75%, ≥90%, and 100% reduction in PASI score (PASI-50, PASI-75, PASI-90, and PASI-100, respectively) at scheduled timepoints (Estimands 5a, 5b, 5c, 5d)

#### 8.2.3.1. Main Analysis Approach

A participant receiving any prohibited medication or discontinuing the treatment due to related adverse event or requirement for prohibited medication will be considered as a non-responder at scheduled timepoints following the event (Composite strategy). If a participant discontinued treatment for reasons other than related adverse event or requirement for prohibited medication, PASI scores reported after the treatment discontinuation date will be treated as missing (Hypothetical strategy). If a participant experienced any treatment interruption, PASI score reported after the treatment interruption will be used as reported (Treatment policy).

Participants without PASI score at each scheduled visit (either due to hypothetical strategy implementation or missed visit) will be considered as non-responder.

The following analyses will be performed using generalized estimating equation (GEE) as an extension of the logistic regression model with treatment, visit and baseline PASI score (as a continuous covariate) as covariates and a treatment by visit interaction. The following additional covariates will be tested in the model using backward elimination with a significance level of 0.2 to retain the covariates in the model: age, BMI and weight as continuous covariates, sex, previous biologic therapy (Yes/No) (as per IRT) and geographic region (North America/Western Europe vs. Eastern Europe) (as per IRT). At the very least, previous biologic therapy and geographic region will be retained in the model. Of note, visits from the earliest timepoint with at least one responder will be included in the model. e.g. if the first responder is on Day 15, all GEE models will include visits from Day 15.

- Participants achieving ≥50% reduction in PASI score (PASI-50) at scheduled timepoints up to Week 12 by treatment group for the FAS. (Estimand 5a)
- Participants achieving ≥75% reduction in PASI score (PASI-75) at scheduled timepoints up to Week 12 by treatment group for the FAS. (Estimand 5b)
- Participants achieving ≥90% reduction in PASI score (PASI-90) at scheduled timepoints up to Week 12 by treatment group for the FAS. (Estimand 5c)

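### SAP 15.2 makes the whole PASI missing when a severity score is blank, even for a region with area score 0, so a fully known Week 12 score could be counted as a PASI-75 non-response

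*SAP*

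**What the plan says.** SAP 15.2 scores three severity items (erythema, induration or thickness, scaling) from 0 to 4 in each of four body regions, and the extent of involvement from 0 (none) to 6. For the calculation it says: "The sum of severity scores for erythema, thickness, and scaling is multiplied by the degree of involvement for each anatomic region". The products are weighted 0.1, 0.2, 0.3 and 0.4 (head, upper limbs, trunk, lower limbs) and summed. The rule for incomplete items is: "The PASI score will be set to missing if any severity score or degree of involvement is missing". It applies to any region, whatever that region's area score.

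A missing score then becomes a failure. SAP 8.1.1.1 says: "Participants without Week 12 PASI score (either due to hypothetical strategy implementation or missed visit) will be considered as non-responder". The Section 8 table treats everyone without observed or imputed Week 12 data as a non-responder, and the PASI-75 definition in 8.1 puts every case that does not meet the 75% criterion in the non-responder class. For PASI-50, -75, -90 and -100 by visit, 8.2.3.1 says: "Participants without PASI score at each scheduled visit (either due to hypothetical strategy implementation or missed visit) will be considered as non-responder".

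**The concern.** When a region is clear, its severity scores carry no information about the PASI, because they are multiplied by an area score of 0. The SAP nevertheless lets a blank in one of them void the whole score. The main analysis then reads that void as treatment failure, although the recorded items already show the participant's response status.

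The rule can be triggered only in a participant with at least one clear region, a state that good response can produce. A Week 12 score lost this way can turn a true responder into a non-responder, but it cannot turn a non-responder into a responder. What is at stake is the primary PASI-75 count and the PASI-50/75/90/100 counts by visit. In the continuous PASI analyses (SAP 8.2.5) the same score would drop out as missing, although its value is known.

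**Working it through.** **Inputs.** The formula, scales and missing-item rule are from SAP 15.2. The non-responder rules are from SAP 8.1, 8.1.1.1, 8.2.3.1 and the Section 8 table. The arm size of about 45 is from SAP 4.2.

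**Formula.** PASI = 0.1(E+I+S)A for head + 0.2(E+I+S)A for upper limbs + 0.3(E+I+S)A for trunk + 0.4(E+I+S)A for lower limbs.

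**The plan's own figure.** With every severity score 4 and every area 6: (0.1 + 0.2 + 0.3 + 0.4) × 12 × 6 = 72. With all scores 0 the result is 0. This reproduces the stated range of 0 to 72.

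**Does a blank matter when the area is 0?** The head term is 0.1 × (E+I+S) × 0 = 0. Each item takes 5 values, so there are 5³ = 125 possible combinations. With the other regions clear, all 125 give PASI 0. The blank leaves nothing unknown.

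**Case 1: two regions clear, residual disease in the other two (illustrative scores).**

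| Region | Baseline E, I, S; A | Term | Week 12 E, I, S; A | Term |
|---|---|---|---|---|
| Head | 2, 2, 2; 1 | 0.1 × 6 × 1 = 0.6 | blank; 0 | 0 |
| Upper limbs | 3, 3, 2; 3 | 0.2 × 8 × 3 = 4.8 | 1, 1, 0; 1 | 0.2 × 2 × 1 = 0.4 |
| Trunk | 3, 3, 3; 3 | 0.3 × 9 × 3 = 8.1 | blank; 0 | 0 |
| Lower limbs | 3, 3, 3; 4 | 0.4 × 9 × 4 = 14.4 | 1, 1, 1; 1 | 0.4 × 3 × 1 = 1.2 |
| **PASI** | | **27.9** | | **1.6** |

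Reduction: (27.9 − 1.6) / 27.9 = 94.3%, a PASI-75 response by the formula. Under the rule as written, the Week 12 PASI is missing and the participant is a non-responder.

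**Case 2: completely clear.** Baseline severity is 2, 2, 2 in every region, with areas 1, 2, 2 and 3 for head, upper limbs, trunk and lower limbs: 0.6 + 2.4 + 3.6 + 7.2 = 13.8. At Week 12 all four areas are 0.
- All severity items entered as 0: PASI 0, a 100% reduction, responder.
- One or more severity items blank: PASI is still 0 by the formula, but the rule makes it missing and the participant a non-responder.

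The two records describe the same skin and receive opposite classifications.

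**Size per participant.** 1/45 = 2.2 percentage points of an arm's response rate.

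**Illustration of power (assumed rates, not in the documents).** This uses the normal approximation for two proportions, 45 per arm, two-sided 5%, with the same fraction of responders lost in both arms.

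| Assumed true rates | No loss | 5% lost | 20% lost |
|---|---|---|---|
| 40% v 10% | 92.1% | 90.2% | 82.4% |
| 30% v 10% | 66.5% | 63.6% | 54.5% |

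The loss fractions are arbitrary. The table shows only that a rare event would cost little and a common one would not be trivial.

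**The case against.** The strongest reply is that the trigger is not shown. Severity has a 0 category, so a clear region has a proper entry (0, 0, 0). Entered that way, the PASI is computed correctly, as Case 2 shows. Collection instructions are in the Study Reference Manual (Protocol 8.1), and the SAP is to be read with an eCRF dated 28 August 2023. Neither is available here, and either may require the zeros. Protocol 10.1.7 also provides for data quality checks and for monitors to verify that entries are complete, so some blanks would be queried and filled. All of this stands: the frequency is unknown and may be zero.

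A second reply is that the sentence in 8.1.1.1 explains a missing Week 12 score only by the hypothetical strategy or a missed visit, not by an attended visit with an incomplete form. That is a fair reading of the sentence. The catch-all in 8.1 and the Section 8 table still lead to non-responder. The text of the sensitivity and supplementary analyses is not visible and may treat such cases differently, but the visible main analysis does not.

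A reader might go further and infer three things that the documents do not support:
- **The primary comparison is biased towards no effect and the dose-response is flattened.** This would follow only if unresolved blanks occur, and occur in enough participants. Nothing in the documents shows that they do.
- **A participant could be left with no baseline PASI.** Eligibility requires PASI of at least 12 at both Screening and Baseline (Protocol 5.1), so this would need incomplete items at both visits in someone confirmed eligible at both.
- **The rule is also wrong for a blank in an involved region.** There the score really is unknown. Setting it to missing is simple and conservative, and it agrees with Protocol 9.5, under which missing dermatology data are not imputed. Keeping a response status that holds for every possible value of the blank item would be a matter of preference.

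**Conclusion.** The point holds as a defect in a derivation rule, not as a demonstrated bias. As written, SAP 15.2 discards a PASI that its own formula fully determines, and the Week 12 rules turn the discarded score into a PASI-75 failure. Whenever the rule is triggered in this way, its result is wrong.

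The conclusion rests on two readings: that the unqualified rule covers regions with area score 0, and that an attended visit with an incomplete PASI falls under the non-responder catch-all. The total effect cannot be estimated from the documents. It is nil if the eCRF forces a 0 and otherwise 2.2 points per lost responder in an arm of 45, always downwards at Week 12.

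**What to change.** Replace the missing-item sentence in SAP 15.2 with wording such as:

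*If the area score of a region is 0, that region contributes 0 to the PASI whether or not its severity scores are recorded. Otherwise PASI is missing when a severity score is blank in a region with area score above 0, or when the area score of any region is blank.*

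Apply it at all visits, including Screening and Baseline, and settle it before unblinding. Setting the term to 0 is arithmetic and not imputation, so it does not conflict with Protocol 9.5.

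The cost is one short SAP paragraph and a small change to the derivation code, with no new data. If the eCRF already requires zeros, the change alters no result.
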